## **6 FOLLOW UP AND OUTCOME EVALUATION**

### **6.1 Follow-Up Schedule**

All participants will be followed every 2 weeks during the intervention. At each visit, patient's performance status and toxicity of treatment will be monitored, and blood test will be checked for complete blood count, liver function, and renal function. Thyroid function test and early morning cortisol (9am) will be performed at least every 4 weeks while on bintrafusp alfa therapy. For female patients in reproductive age, urine or serum pregnancy test needs to be performed at least every month while the subject is on bintrafusp alfa therapy. All adverse events and laboratory abnormalities will be graded per the National Cancer Institute Common Terminology Criteria for Adverse Events, version 4.0.

For blood-borne immune markers and exploratory biomarkers, plasma EBV DNA will be determined before treatment and every 2 weeks until disease progression; plasma TGF $\beta$ 1 measurement will be performed every 8 weeks until disease progression; exo-PD-L1 concentration will be measured every 2 weeks until disease progression.

Tumor imaging by CT head, neck, chest, abdomen, and pelvis will be done at baseline, every 8 weeks for the first 12 months, then every 12 weeks thereafter. Response will be assessed per RECIST version 1.1. Treatment decisions will be based on Investigator(s) review.

## 6.2 Outcome Measures

Primary outcome:

- Objective response rate (ORR): The percentage of patients with radiologically complete or partial response as determined by the Investigator according to RECIST version 1.1.

Secondary outcomes:

- Progression-free Survival (PFS): PFS is measured from the date of informed consent to radiographically documented progression according to RECIST 1.1 or death from any cause (whichever occurs first). Participants alive and without disease progression or lost to follow-up will be censored at the date of their last radiographic assessment
- Time to progression (TTP): TTP is measured from the date of informed consent to radiographically documented progression according to RECIST 1.1. Participants death and without disease progression, alive without disease progression, or lost to follow-up will be censored at the date of their last radiographic assessment
- Overall survival (OS): OS is measured from date of informed consent to the date of death from any cause. Participants alive or lost to follow-up will be censored at the date of their last radiographic assessment

Survival rate at 12 months and 24 months: The percentage of study population who are still alive for 12 months and 24 months from the date of study enrollment. Participants alive or lost to follow-up will be censored at the date of their last radiographic assessment

Duration of response (DOR): DOR is the time from documentation of tumor response to radiographically documented disease progression

- ORR, TTP, and PFS of the same definitions as above are measured against immune-related RECIST (irRECIST) criteria as one of the secondary endpoints.
- Safety outcome measures: Incidence, nature, and severity of adverse events graded according to the National Cancer Institute Common Terminology Criteria for Adverse Events (NCI-CTCAE v.4)
- Pre-treatment, serial post-treatment plasma EBV-DNA levels, and dynamics of

EBV DNA levels will be measured

- Disease control rate (DCR): The percentage of patients with a CR, PR, or SD  $\geq$  6 months per RECIST 1.1
- Time to response (TTR): TTR is measured from the date of informed consent to first radiographically documented tumor response per RECIST 1.1
- Quality of life (QoL): as assessed by the European Organization for Research and Treatment of Cancer Core Quality of Life Questionnaire (EORTC-QLQ-C30) and the head and neck cancer-specific H&N-35 questionnaires

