### 7.2 Sample Size Calculation

H0: The null hypothesis is that the overall response rate (ORR) is similar to historical result of immunotherapy, i.e. 20%

H1: The alternative hypothesis of treatment efficacy: experimental treatment with bintrafusp alfa would result in 40% ORR.

To detect 20% of differences from 20% to 40% in the number of patients proceeding to surgery, with Type I error of 0.05 and 80% power, the target sample size is 33 patients.

Modified Simon's two-stage optimal design will be used. In the first stage, 18 patients will be enrolled. If there are 4 or fewer responses in these 18 patients, the study will be stopped. Otherwise, 15 additional patients will be accrued for a total of 33 valid cases. The null hypothesis will be rejected if 11 or more responses are observed in 33 patients and the treatment will be considered worthy of further investigation. Patients may drop out before their objective response can be assessed. Such patients will be excluded for the ORR assessment and will be replaced by other patients that the objective response can be assessed. The study will be continued until the first or the second stage evaluation is achieved. Assuming 10% drop out rate, 38 patients will be accrued initially. We assume 50% of screened population will be eligible for the study, thus we plan to screen for 76 patients.

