### **8.3 Informed Consent**

The consent of the patient to participate in the clinical study has to be given in writing before any study-related activities are carried out. It must be signed and personally dated by the patient and by the Investigator(s)/person designated by the Investigator(s) to conduct the informed consent discussion.

Provision of consent will be confirmed in the case report form (CRF) by the Investigator(s). The signed and dated declaration of informed consent will remain at the Investigator(s)'s site and must be safely archived by the Investigator(s) so that the forms can be retrieved at any time for monitoring, auditing and inspection purposes. A copy of the signed and dated information and consent should be provided to the patient prior to participation.

If the patient or legally acceptable representative is unable to read, a reliable, impartial, and independent witness should be present during the entire informed consent discussion. The choice of the witness must not breach the subject's right to confidentiality. A reliable independent witness is defined as one not affiliated with the institution or engaged in the investigation. A family member or acquaintance is an appropriate independent witness. After the subject or legally acceptable representative verbally consents and has signed, if capable, the witness should sign and personally date the consent form attesting that the information is accurate and that the subject or legally acceptable representative has fully understood the content of the informed consent agreement and is giving true informed consent.

Also, patient will be informed in a timely manner whenever new information becomes available that may be relevant to the patient's willingness to continue participation in the study; the revised informed consent form containing such information is to be provided to the patient, and communication of this information will be documented.

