## 11 APPENDIX Schedule of Assessments

Procedures	Screening	Treatment Period (bintralusp alfa until PD; unacceptable toxicity; death or withdrawal; maximum of 2 years)										Disease Progression
		Cycle 1 m Cycle = 14 Days ± 7 Days		Cycle 2	Cycle 3	Cycle 4	Cycle 5	Cycle 6	Cycle 7	Cycle 8	Cycle 9 and thereafter	
		Day -28 - 0	Day 1	Day 1	Day 1	Day 1	Day 1	Day 1	Day 1	Day 1	Day 1	
Tests and Observations												
Informed Consent d	x											
Medical History	x											
Physical Examination (including skin examination) e	x	x	x	x	x	x	x	x	x	x	x a	x
Vital Signs	x	x	x	x	x	x	x	x	x	x	x a	x
ECOG Performance Status	x	x	x	x	x	x	x	x	x	x	x a	x
ECG	x	x				x					x b	x
Adverse Event Evaluation	x	x	x	x	x	x	x	x	x	x	x a	x
Concomitant Medication Review	x	x	x	x	x	x	x	x	x	x	x a	x
Laboratory Tests												
CBC f	x	x	x	x	x	x	x	x	x	x	x a	x
Coagulation Test h	x	x	x			x	x	x	x	x	x b	x
Comprehensive Serum Chemistry Panel g	x	x	x	x	x	x	x	x	x	x	x a	x
Exploratory blood-based biomarkers i	x	x i	x	x i	x	x i	x	x i	x i	x	x i	x
Urinalysis	x	x	x	x	x	x	x	x	x	x	x a	x
Pregnancy Test j	x						x				x c	x
Thyroid Function Test		x		x		x		x		x	x c	x
Cortisol 9AM		x		x		x		x		x	x c	x
Disease Assessment												
CT Scan (Head, Neck, Chest, Abdomen, Pelvis) k	x	x				x				x k	x	
MRI Scan (Brain)												
Survival follow-up	x		x				x					x
Quality of life assessment l	x		x				x				x	x

- a. Assessments/procedures are to be performed on Day 1 every cycle and prior to treatment unless otherwise specified.
- b. Assessments and procedures are to be performed on Day 1 every 4 cycles and prior to treatment unless otherwise specified.
- c. Assessments and procedures are to be performed on Day 1 every 2 cycles and prior to treatment unless otherwise specified.
- d. Informed Consent must be obtained  $\leq$  28 days prior to the initiation of trial treatment.
- e. Physical examinations will include measurements of weight and vital signs (resting heart rate, blood pressure, respiratory rate, temperature).

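### PFS, TTP, OS and TTR start at informed consent, 0 to 28 days before first dose, while the 12- and 24-month survival rates start at an undefined study enrollment date

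*Protocol*

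**What the plan says.** Section 6.2 of the protocol gives four secondary endpoints the same start date:

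- PFS: "PFS is measured from the date of informed consent to radiographically documented progression according to RECIST 1.1" (or death).
- TTP: "TTP is measured from the date of informed consent to radiographically documented progression according to RECIST 1.1".
- OS: "OS is measured from date of informed consent to the date of death from any cause".
- TTR: "TTR is measured from the date of informed consent to first radiographically documented tumor response per RECIST 1.1".

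The same section words the origin of the survival rates differently. They are the percentage alive at "12 months and 24 months from the date of study enrollment". The term is not defined.

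Three other places fix how far consent lies from treatment and who gets from one to the other:

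- Section 8.3: "The consent of the patient to participate in the clinical study has to be given in writing before any study-related activities are carried out". Consent therefore comes before screening.
- Appendix, Schedule of Assessments, note d: consent is obtained no more than "28 days prior to the initiation of trial treatment".
- Sections 4.2 and 7.2: eligibility is confirmed at registration, before treatment begins. "We assume 50% of screened population will be eligible for the study", so 76 are to be screened to accrue 38.

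Section 7.1 estimates TTP, PFS, OS and the survival rate by Kaplan-Meier with 95% confidence intervals.

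**The concern.** The clock starts before it is known whether a patient will enter the trial. Someone who dies or proves ineligible between consent and registration does not become one of the 38. Among the 38, that interval cannot contain a death, yet it is counted in OS, PFS and TTP. Its length depends on how quickly the site completes screening and says nothing about bintrafusp alfa.

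The trial has one arm, so no control group carries the same lead-in. The effect is proportionally largest for PFS and TTP, because the Background puts second-line TTP at only about 4 months. For TTR it runs the other way: the lead-in delays the apparent response.

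The second issue is consistency. OS and the 12- and 24-month survival rates describe the same events but have differently worded origins. Unless study enrollment means the consent date, a 12-month rate computed as defined need not equal the value of the OS curve at 12 months.

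**Working it through.** **The plan's own figures.** The two-stage ORR design continues with 5 or more responses in 18 and rejects with 11 or more in 33. Summing exact binomial probabilities over the stage-one outcomes gives a rejection probability of 0.0458 at a 20% response rate and 0.8011 at 40%. The stated 0.05 and 80% reproduce. The screening figure also reproduces: 38 / 0.50 = 76. Neither calculation uses a time origin, so neither depends on this point.

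**Inputs.** Lag d from consent to first dose: 0 to 28 days (Appendix, note d). The actual lag is not given, so 14 days is an assumed middle value. Illustrative medians from the Background: TTP about 4 months; PFS/TTP 5.1 months (gemcitabine, Table 1); OS 12.8 months (docetaxel, Table 1). Illustrative landmark rates from the Background: 12-month PFS 19.3% and OS 59% (nivolumab study); 6-month PFS 49.7% (pembrolizumab study). These serve only as scale.

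**Lead-in in months.** d / 30.44: 14 / 30.44 = 0.46; 28 / 30.44 = 0.92.

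**Medians.** If every analysed patient has lag d, the median from consent is the median from first dose plus d.

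| Lag | Median 4.0 | Median 5.1 | OS median 12.8 |
|---|---|---|---|
| 0 days | 4.00 | 5.10 | 12.80 |
| 14 days | 4.46 (+11.5%) | 5.56 (+9.0%) | 13.26 (+3.6%) |
| 28 days | 4.92 (+23.0%) | 6.02 (+18.0%) | 13.72 (+7.2%) |

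**Landmark rates.** For patients certain to survive the lag, the rate at time t from consent is S(t − d), with S measured from first dose. Taking S as exponential, S(t) = exp(−λt) and λ = −ln S(t) / t. Example: for S(12) = 0.193, λ = 1.645 / 12 = 0.1371 per month, and S(12 − 0.92) = exp(−0.1371 × 11.08) = 0.219.

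| Rate | d = 0 | d = 14 days | d = 28 days |
|---|---|---|---|
| 12-month PFS | 19.3% | 20.6% | 21.9% |
| 6-month PFS | 49.7% | 52.4% | 55.3% |
| 12-month OS | 59.0% | 60.2% | 61.4% |

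**TTR.** A response first seen on a scan 8 weeks after first dose has TTR 56 / 30.44 = 1.84 months from dose, but up to (56 + 28) / 30.44 = 2.76 months from consent. Counting the 8 weeks from first dose is an assumption made for this example.

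**Scale against sampling error.** With 38 patients and no censoring, the approximate 95% half-width is 1.96 × √(0.59 × 0.41 / 38) = 0.16 for the 12-month OS rate and 1.96 × √(0.193 × 0.807 / 38) = 0.13 for the 12-month PFS rate. At their largest, the shifts are 2.4 and 2.6 points.

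**The case against.** The strongest reply is that nothing decisive rests on these endpoints. The study hypothesis and the test in section 7.2 concern response rate only. PFS, TTP and OS are secondary and descriptive, with no historical threshold. That stands, and it limits the severity.

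A reader might go further and infer that the trial credits its patients with extra time against historical results. The documents do not support that. No such comparison is planned, and the time origins of the cited studies are not given. If those studies also counted from registration or enrolment, some or all of the difference would vanish. What remains is that the Background does weigh earlier agents by TTP and survival, so an informal reading of this kind is foreseeable.

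Guaranteed time also depends on the analysis set, which the protocol does not name for these endpoints. If everyone who consented were analysed, there would be none. The accrual plan points the other way, to 38 of 76. The reference in section 6.4 to following consenting patients concerns those who withdraw from treatment, not screen failures. The 50% figure is a screening yield, not evidence of early deaths, and it does not enter the calculation.

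Other inferences also go too far. TTR is not credited; it is penalised. Twenty-eight days is a ceiling, not a typical lag. The documents do not clearly anchor the CT schedule to first dose. Two separate survival curves are not shown either: section 7.1 lists OS and survival rate together under Kaplan-Meier, and study enrollment could turn out to mean the consent date. The demonstrable fault there is an undefined, differently worded origin.

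**Conclusion.** The point holds as a defect in a rule that section 6.2 states outright. In accrued or treated patients, consent-based timing adds a drug-independent interval to PFS, TTP and OS. The addition is 0 to 0.92 months if treated patients are analysed; if registered patients are analysed, only the part up to registration is guaranteed. It matters for a median near 4 months (up to +23%, or +11.5% at an assumed 14 days) and little for OS (up to +7.2% on 12.8 months). The landmark shifts are about 2 to 6 points at most and rest on the exponential assumption; the 12-month shifts are well inside sampling error. Unlike sampling error, however, they always go in the same direction. TTR is made to look later. Separately, the survival rates lack a defined origin that matches OS.

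The conclusion assumes that the analysis set is the accrued or treated patients. It does not extend to the ORR test, the sample size, the power or a quantified bias against the cited studies. Severity is minor to moderate: secondary endpoints only.

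**What to change.** In section 6.2, use one origin for PFS, TTP, OS, TTR and the 12- and 24-month survival rates: the date of the first bintrafusp alfa dose (Cycle 1 Day 1), analysed in treated patients. Registration date in registered patients would also be acceptable. What matters is that origin and analysis set are named together and match. Replace the study enrollment wording accordingly and state that the 12- and 24-month rates are read from the OS Kaplan-Meier curve. The irRECIST versions of PFS and TTP follow automatically, since section 6.2 gives them the same definitions.

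The change is to wording only. Reported PFS, TTP and OS medians become slightly shorter, by at most 0.92 months.

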### **6.4 Criteria for Removal from Protocol Treatment**

- Disease progression
- Inter-current disease that would affect assessments of clinical status to a significant degree, require discontinuation of drug, or both.
- Unacceptable toxicity.
- The patient may withdraw from treatment at any time for any reason. The reason should be recorded. Follow-up will be continued for all consenting patients for up to 2 years.

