- f. Hematology parameters include the following laboratory tests: complete blood count with 3-part differential (i.e. total neutrophil count including bands, lymphocytes, and monocytes), hemoglobin, hematocrit and platelets.
- g. Blood chemistry must include glucose, BUN, creatinine (eGFR), sodium, potassium, magnesium, chloride, calcium, CO2, alkaline phosphate, AST (SGOT), total bilirubin, total protein, albumin, phosphorus, uric acid.
- h. Coagulation test include PT, PTT and INR.
- i. Plasma EBV DNA will be determined before treatment and every 2 weeks until disease progression; plasma TGF $\beta$ 1 measurement will be performed every 8 weeks until disease progression; PD-L1 concentration in the exosome will be measured every 2 weeks until disease progression.
- j. Pregnancy test will be performed within 1 week prior to treatment, if a cycle is missed during treatment or pregnancy and at the end of treatment visit only for women of childbearing potential.
- k. Patients will have CT scan at Screening/Baseline ( $\leq$  28 days prior to initiation of trial treatment), every 8 weeks for the first 12 months, and every 12 weeks thereafter. Patients will also have CT scan whenever disease progression is suspected. For patients who discontinue treatment without radiographic progression per RECIST 1.1 (e.g. in patients who discontinue treatment for clinical progression or adverse reactions), disease assessment should continue as stated in schedule until radiographic disease progression or alternate therapy is given.
- l. Quality of life (QoL) will be assessed by patient-reported EORTC QLQ-C30 and H&N-35 questionnaires every 12 weeks in the first year.
- m. If screening assessments were completed within 28 days, they do not need to be repeated on Day 1 of Cycle 1 if patient's condition has not changed.

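### PFS has no rule for alternate therapy started before RECIST progression, while scheduled scans stop at that point, so patients who fail clinically and switch are handled favourably in PFS and TTP

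*Protocol*

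**What the plan says.** Four parts of the protocol bear on this.

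- **PFS event (6.2).** PFS runs from informed consent to "radiographically documented progression according to RECIST 1.1 or death from any cause (whichever occurs first"). Clinical progression is not an event, and a death counts however long after a change of therapy it falls.
- **Censoring (6.2).** For PFS: "Participants alive and without disease progression or lost to follow-up will be censored at the date of their last radiographic assessment". For TTP: "Participants death and without disease progression, alive without disease progression, or lost to follow-up will be censored", again at the last scan. Neither rule mentions alternate therapy. The irRECIST versions of PFS and TTP take the same definitions.
- **Scans (6.1; Appendix, footnote k).** CT is done "every 8 weeks for the first 12 months, then every 12 weeks thereafter". For patients who stop without radiographic progression, with the example "in patients who discontinue treatment for clinical progression or adverse reactions", the footnote says that "disease assessment should continue as stated in schedule until radiographic disease progression or alternate therapy is given". It also says: "Patients will also have CT scan whenever disease progression is suspected".
- **Follow-up (6.4).** After withdrawal from treatment: "Follow-up will be continued for all consenting patients for up to 2 years". Section 6.3 has all causes of death recorded.

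**The concern.** The definition of PFS presumes that progression can be seen until it happens. Footnote k ends the scheduled scans at the start of alternate therapy, while death goes on being counted for up to 2 years. For a patient who fails clinically without a RECIST event and then switches, the PFS result depends on survival under another treatment. If he dies in follow-up, the months after the switch count as progression-free. If he lives, he leaves the risk set at a scan before his failure, although the reason for leaving is that he was failing. Both outcomes raise the PFS curve.

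PFS and TTP are the first two secondary objectives. In a single-arm trial, readers will set them beside the historical figures in section 1. There the salvage regimens in Table 1 lie between 4.9 and 5.3 months, and one-year PFS on checkpoint inhibitors is 19.3% and 30.1%.

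**Working it through.** The protocol gives no PFS sample size, event count or power, so there is no figure of its own to reproduce. The check is a trace of the rules, followed by an illustration of size.

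**1. One patient.** He has clinical progression and switches at month 4. The last scan is at week 16 (16 × 7 / 30.44 = 3.7 months) and shows no RECIST progression.

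| Outcome | PFS as written | TTP as written | Clinical progression counted |
|---|---|---|---|
| Dies at month 14 | event at 14 | censored at 3.7 | event at 4 |
| Alive at month 24 | censored at 3.7 | censored at 3.7 | event at 4 |

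In the first row, 14 − 4 = 10 months on another therapy count as progression-free. In the second row there is no credit, but the failure disappears. TTP never receives the credit.

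**2. Inputs for size.**
- From the protocol: one-year PFS of 19.3% on nivolumab (section 1), follow-up of 24 months, scans every 8 weeks.
- Assumed: exponential progression; median survival after progression of 9 months; a share f of progressions that are clinical only and followed by a switch. The document does not give f, so it is set at 5%, 10% and 20%.

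Hazard λ = −ln(0.193)/12 = 0.137 per month, so the true median is ln 2/0.137 = 5.06 months.

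**3. Hand check.** If the share f is censored at the moment of failure, the Kaplan-Meier curve estimates exp(−(1 − f)λt), and the median becomes 5.06/(1 − f). That is 5.06/0.95 = 5.3, 5.06/0.90 = 5.6 and 5.06/0.80 = 6.3 months.

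**4. Simulation of the rules** (one million patients per case):

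| f | Median PFS as written | Median if censored at last pre-switch scan | 12-month PFS as written | 12-month PFS if censored |
|---|---|---|---|---|
| 0 | 5.06 | 5.06 | 19% | 19% |
| 5% | 5.34 | 5.29 | 21% | 21% |
| 10% | 5.64 | 5.55 | 23% | 22% |
| 20% | 6.34 | 6.17 | 27% | 26% |

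At f = 20%, post-progression medians of 6 or 12 months give 6.2 or 6.4 months. The censored median is also what TTP would read in this model.

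**5. Where the shift comes from.** At f = 20%, the whole shift is 6.34 − 5.06 = 1.28 months. Without any survival credit it is 6.17 − 5.06 = 1.11 months, or 1.11/1.28 = 87% of it. At 10% the ratio is 0.49/0.58 = 84%, and at 5% it is 0.23/0.28 = 82%. Most of the shift comes from not counting clinical failure.

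**6. A second model.** Progression is detected only at the protocol's scans (8-weekly, then 12-weekly), 10% of first events are deaths (assumed), and a post-progression hazard of 0.085 per month gives one-year OS of about 59%, the figure quoted for nivolumab. Twelve-month PFS:

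| f | As written | Clinical progression counted | Censored at last pre-switch scan |
|---|---|---|---|
| 5% | 23.0% | 21.4% | 22.9% |
| 10% | 24.7% | 21.5% | 24.5% |
| 20% | 27.7% | 21.2% | 27.7% |

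About 75% of switchers die within 24 months in this model. The pattern is the same.

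**The case against.** The strongest reply is that a rule for new therapy is ordinary SAP content, and that counting RECIST progression or any death regardless of therapy is a recognised definition. This holds in part. But that definition needs scans to continue after a switch, and the protocol itself ends them. Event, censoring and scan stop are all fixed here. Section 7.1 refers the imputation of missing data to the SAP, and has changes to key secondary endpoints made by protocol amendment.

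Second, footnote k requires a CT whenever progression is suspected. A patient whose CT then shows RECIST progression has his event at the right time. This stands, and it reduces the number affected. It does not bring it to zero, because the same footnote foresees stopping for clinical progression without radiographic progression.

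Third, the effect may be small beside sampling error. With 38 patients, 10% is about four. The sampling SD of a 5.1-month median is then about 1.2 months, against a shift of about 0.6. This stands too, but the shift is in one direction and can be avoided.

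Some stronger readings are tempting but not supported:
- That credited survival is the main bias. Step 5 shows otherwise.
- That progression cannot be recorded after a switch. Only scheduled scans end; later routine imaging is not barred.
- That every affected patient is failing. The footnote also names adverse reactions.
- That the comparison with section 1 is biased by a known amount. The document does not give the PFS rules of those studies.

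**Conclusion.** The point holds as a fault in how secondary endpoints are defined, and it should be corrected. Followed exactly, sections 6.2 and 6.4 and footnote k overstate PFS whenever a patient fails clinically, switches and has no RECIST progression documented. TTP and both irRECIST versions share the informative censoring; only PFS, by either criterion, adds survival credit, and only for switchers who die in follow-up.

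The size depends on a share that the document does not give. At an assumed 5%, 10% or 20% of progressions, median PFS reads about 5.3, 5.6 or 6.3 months instead of 5.1, under exponential progression at the nivolumab rate and 9 months' median survival afterwards. These figures illustrate the direction and order of the effect; they do not forecast this trial's result.

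A reader might infer that the trial's conclusion is at risk. It is not: the go/no-go rule in section 7.2 rests on ORR alone, and PFS and TTP carry no hypothesis test or decision rule.

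**What to change.** 1. State in 6.2 one rule for alternate therapy started before RECIST progression, such that a death after the switch is not a PFS event at the death date. It must cover patients who stopped for clinical progression and those who stopped for an adverse reaction.
2. Prespecify for PFS and TTP an analysis in which documented clinical progression followed by alternate therapy is an event at the earlier of the two dates. Patients who switch after an adverse reaction are censored at the last scan before the switch. Report it beside the RECIST-only analysis.
3. Do not make censoring at the last scan the only sensitivity analysis. In the illustrations it leaves nearly all of the shift.
4. Record in the CRF the reason for stopping and the start date of alternate therapy.

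The cost is a paragraph in 6.2 and two CRF items, of which the reason for stopping is partly covered by 6.4. No extra scans are needed. PFS may read slightly lower, and the added analysis relies on the investigator's judgement of clinical progression in an uncontrolled trial. That is why it stands beside the RECIST-only analysis and does not replace it.
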